4. **Intervention feasibility:** We have conducted several tests to ensure smooth implementation of our proposed intervention. First, we have verified that patients have a very high probability of actually receiving pre-appointment letters or postcards. To evaluate this, [name] used administrative data to construct a sample of 1,110 VAPORHCS patients who had had an in-person primary care visit and positive depression screen in the last year. Of these patients, postal

addresses were correct for 95.6% based on phone and postal verification efforts. Second, we have confirmed that the vast majority of appointments are scheduled at least two weeks in advance, which is a timeframe used to determine whether to mail a reminder letter or postcard. To determine this, we extracted data comparing scheduled appointment “create date” and appointment date. Results from the VSSC pending appointment report showed that in July 2016, 92.8% of all VHA scheduled appointments nationally in mental health were created at least two weeks in advance (94.7% in primary care), with similarly high rates at VAPORHCS.

5. **Pilot effectiveness study:** We conducted a pilot effectiveness study of a version of the most basic proposed intervention. Reminder templates were changed on July 1, 2016 in randomly selected mental health clinics across VAPORHCS, and no-show rates were compared between intervention and control clinics in the pre-(April-June 2016) and post-intervention (July-Sept. 2016) periods. Difference-in-difference results showed an absolute decrease of 0.6% in no-shows, and 3.8% increase in appointment attendance in association with the intervention. This suggests that in three months in just a handful of clinics, over 100 no-shows were averted by making a one-time change to pre-appointment reminder templates. Assuming this same effect size and application to all mental health and primary care clinics in VAPORHCS, we estimate this basic intervention alone could avoid over 1,500 no-shows [.006*(102,060 mental health + 157,587 primary care appointments/year)].

Research Design and Methods

A. Design Overview:

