K. Power Analyses: For our Aim 2 and Aim 3 power calculations, we used FY2016 stop code-level no-show rates at each of the eight locations and the provider-level number of scheduled appointments at each location to conduct Monte Carlo simulations. We assumed two possible differences in no-show and cancellation rates for the interventions (1.9% and 2.7%), which represent changes in appointment attendance on par with our pilot data and two prior RCTs using similar variations in BE messages in appointment reminders³¹. Because baseline no-show rates in the RCTs were lower than ours, leading to possible floor effects, these estimated effects are relatively conservative⁹⁴. We assumed a total of 256 providers randomized to the interventions. In addition, to account for intra-class correlation among providers and the effects of over-dispersion, we allowed for correlated binary measurements to be correlated with parameter $\rho = (\sigma_b^2/\sigma_b^2 + \pi^2/3)$. We varied ρ between two and five percent. All hypothesis tests were two-sided, with no adjustments for multiple comparisons. As the

number of providers, patients and scheduled appointments within providers and no-show rates differ between primary care and mental health, separate Monte Carlo simulations were performed to address power and sample size requirements for the two specialties. Each simulation was run a minimum of 500 times. We calculated power as the proportion of times the stated statistical hypothesis was correctly rejected.

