Power calculations are conducted separately for primary care and mental health. In primary care, results of the power analyses show that there is >99% power to detect a no-show rate difference of 2.7% between the intervention and usual care, and 82% power to detect a no-show rate difference of 1.9% (2.7%-0.6%) between two interventions. In mental health, results of the power analyses demonstrate that there is 80% power to detect a no-show rate difference of 2.7% between the intervention and usual care, and 45% power to detect a no-show rate difference of 1.9% (2.7%-0.6%) between two intervention groups. In summary, the power analyses demonstrate it is possible to detect relatively modest effects in our Aim 2 outcomes (i.e., 2.7% differences in no-show or cancellation rates between interventions and usual care); it may also be possible to detect smaller effects in our Aim 3 outcomes (e.g., 1.9% differences in no-show or cancellation rates between different intervention arms).

L. Limitations and Alternatives

Single-site effectiveness study: We considered whether to design this study as a multi-site trial to address concerns about external validity. Ultimately, we favored testing our interventions across one VA Health Care System for three reasons. First, a single site allows us to examine effectiveness across two distinct specialties (mental health and primary care), which would be much more difficult in a multi-site study given resource limits. Second, given potential for differing appetites for intervention implementation across VHA sites, we agree on the need for a multi-site study, but see this as best pursued in a subsequent trial. Such a trial could be a multi-site hybrid type 2 trial⁹⁵ informed by the effectiveness (**Aims 2 and 3**) and pre-implementation data (**Aim 4**) from the current proposal to then evaluate multi-site effectiveness and implementation strategies. Third, our single site provides adequate power for our proposed analyses.

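### Section K derives the 1.9% Aim 3 difference from a subtraction that gives 2.1%, and the plan's claim of adequate power does not hold for the mental health Aim 3 comparison, which section K puts at 45%

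*Combined protocol and SAP*

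**What the plan says.** Section K (Power Analyses) names two differences for the simulations: "We assumed two possible differences in no-show and cancellation rates for the interventions (1.9% and 2.7"%). It describes them as values "which represent changes in appointment attendance on par with our pilot data and two prior RCTs", and adds that, because of possible floor effects in those trials, "these estimated effects are relatively conservative".

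For comparisons with usual care at 2.7 points (Aim 2), it reports power above 99% in primary care and 80% in mental health. For comparisons between two interventions (Aim 3), it reports "82% power to detect a no-show rate difference of 1.9% (2.7%-0.6%) between two interventions" in primary care and "45% power to detect a no-show rate difference of 1.9% (2.7%-0.6%) between two intervention groups" in mental health. Its summary is cautious on Aim 3: "it may also be possible to detect smaller effects in our Aim 3 outcomes".

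Section L (Limitations and Alternatives) gives as its third reason for a single site that "our single site provides adequate power for our proposed analyses". Section A (Design Overview, Sites) likewise describes the power for the analyses as sufficient, and says that the two specialties will be analysed separately. Section J lists the pairwise Aim 3 comparisons among the planned hypothesis tests.

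**The concern.** The difference to which 82% and 45% belong is printed in two incompatible ways, once for each specialty, so a reader cannot tell whether the trial was simulated at 1.9 or at 2.1 points. The bracket need not be a typing error: 0.6 is also the pilot's no-show change, so 2.7 − 0.6 could be a deliberate contrast between a strong and a weak arm. Section K does not explain it.

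Separately, the general statements in sections A and L cover all proposed analyses. Aim 3 in mental health is one of them, and section K gives it slightly less than an even chance of detecting the stated difference. With four intervention arms there are six such contrasts per specialty. A non-significant mental health contrast could be read as evidence that two messages work equally well, when the plan's own figures say that the comparison was weak.

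**Working it through.** **1. The subtraction.** Inputs: 2.7 and 0.6, section K.
- 2.7 − 0.6 = 2.1. The printed result is 1.9, which would need 2.7 − 0.8.
- Rounding: 2.7 lies in 2.65–2.75 and 0.6 in 0.55–0.65, so the difference lies between 2.65 − 0.65 = 2.0 and 2.75 − 0.55 = 2.2. Rounding does not explain 1.9.

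**2. Which difference do the stated powers fit?** The plan's powers cannot be reproduced directly. The baseline rates, the split of providers by specialty and the intra-class correlation behind each figure are not given. I therefore back-calculated a standard error (SE) from each stated power, assuming two-sided alpha 0.05 and an SE that does not change with the difference:
- SE = d / (1.96 + z_power)
- power(d) = Φ(d/SE − 1.96) + Φ(−d/SE − 1.96)
- z_power is 0.915 for 82%, −0.126 for 45% and 0.842 for 80%.

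| Stated power belongs to | SE | Power at 1.9 | Power at 2.1 | Power at 2.7 | Plan states at 2.7 |
|---|---|---|---|---|---|
| Primary care, 82% at 1.9 | 1.9/2.875 = 0.661 | 82% | 88.8% | 98.3% | >99% |
| Primary care, 82% at 2.1 | 2.1/2.875 = 0.730 | 73.9% | 82% | 95.9% | >99% |
| Mental health, 45% at 1.9 | 1.9/1.834 = 1.036 | 45% | 52.7% | 74.1% | 80% |
| Mental health, 45% at 2.1 | 2.1/1.834 = 1.145 | 38.2% | 45% | 65.5% | 80% |

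In both specialties the 1.9 rows come closer to the plan's figure at 2.7. That favours 1.9 as the simulated value but does not prove it: with 500 runs the Monte Carlo standard error of a 45% power is √(0.45 × 0.55/500) = 2.2 points, and the constant-SE model is only approximate.

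Starting instead from the stated 80% at 2.7 in mental health: SE = 2.7/2.802 = 0.964, giving 50.5% at 1.9 and 58.7% at 2.1.

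**3. Does any reading rescue the adequacy claim?** Mental health Aim 3 power is 38% (45% belongs to 2.1, power wanted at 1.9), 45% (as stated), or 53–59% (1.9 simulated, 2.1 intended). None reaches 80%.

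**4. Basis of the effect sizes (clarification only).** Preliminary Studies, item 5, reports an "absolute decrease of 0.6% in no-shows, and 3.8% increase in appointment attendance". Section I defines the primary denominator as no-shows plus completed visits, although its opening sentence refers to all scheduled appointments. On a no-shows-plus-completed denominator the two shares sum to 100%, so a 0.6-point fall in no-shows would have to be a 0.6-point rise in attendance. The pair −0.6/+3.8 cannot both be on that scale.

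To convert, let n and a be the no-show and attended shares of scheduled appointments, and read 3.8% as absolute:
- change = n/(n + a) − (n − 0.006)/[(n − 0.006) + (a + 0.038)]
- With r the no-show rate on the no-shows-plus-completed denominator and c the cancelled share, n = r(1 − c) and a = (1 − r)(1 − c).
- r = 9%, c = 15%: 1.0 points. r = 18%, c = 30%: 1.6 points. r = 20%, c = 40%: 2.0 points.
- Taking the shares directly, n = 20% and a = 50% (so r = 28.6%): 2.1 points.

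Under these assumed shares the pilot corresponds to roughly 1.0–2.1 points. That range can reach 1.9 but not 2.7.

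**The case against.** The best defence is that nothing is hidden. Section K prints the 45% just above section L and claims only that smaller Aim 3 effects may be detectable. Section L's sentence is one of three reasons for a single site, not a power statement in its own right. If 1.9 was simulated, as seems likely, the 82% and 45% stand as printed and the error is confined to a bracket. If 2.1 was the intended contrast, the plan understates its power. All of this is fair. It limits the consequences, but the subtraction is still wrong in two places and the adequacy claim is still contradicted by the plan's own figure.

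Three stronger readings are tempting, and the documents do not support them.

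- **That 1.9 and 2.7 are too large.** The pilot tested a version of only the most basic intervention, so planning for more in arms that combine several nudges is a legitimate choice. The two earlier trials may support the sizes, but their figures are not in the documents. Whether the converted pilot effect falls below 1.9 depends on no-show and cancellation shares that the plan does not give.
- **That a null mental health result could not be interpreted.** Section K already gives 80% power at 2.7 points against usual care, so such a result can be placed.
- **That 256 simulated providers contradicts 275 plus 150.** The counts may come from different years, providers can be randomized more than once, and they can opt out. This needs an explanation but is not shown to be an error.

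**Conclusion.** Two statements are wrong as written. First, the 1.9% Aim 3 difference does not follow from 2.7% − 0.6%, which is 2.1%. The bracket is the likelier slip, but the sponsor must confirm it. Depending on the answer, the power that belongs with the intended difference ranges from about 74% to 89% in primary care and from about 38% to 59% in mental health. Second, the adequacy statements in sections A and L do not hold for the mental health Aim 3 comparison, which stays below 80% on every reading.

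The subtraction and the contradiction rest on the plan's printed figures alone. The alternative powers rest on two-sided alpha 0.05 and a constant SE, and are approximate. The effect-size question remains a request for clarification, since no document puts the pilot's figures on the primary-outcome scale. Aim 2 at 2.7 points is supported by section K in both specialties, and nothing here undermines that. The point should be fixed; it does not threaten the design.

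**What to change.** 1. Check which difference was simulated for Aim 3. Correct either the bracket or the difference in both places, and quote the power that belongs to it.
2. In sections A and L, limit the adequacy statement to the comparisons that reach about 80% on section K's figures: Aim 2 at 2.7 points in both specialties, and Aim 3 at 1.9 points in primary care only (subject to step 1). Say plainly that mental health Aim 3 is underpowered.
3. In section J, state that non-significant mental health Aim 3 contrasts will be reported with 95% confidence intervals and not read as equivalence.
4. As clarification, state the basis of 1.9 and 2.7 on the primary-outcome denominator, with the no-show figures of the two earlier trials, and reconcile section I's two wordings of that denominator. Say how 256 providers relates to 275 and 150, by specialty. Simulated power at one smaller effect would be a useful addition but is optional.

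The cost is checking one simulation input and editing a few sentences, plus a re-run of the existing simulation if 2.1 proves to be the intended difference or the optional figure is added. Sample, design and analysis model do not change. The plan's claim about power becomes narrower.
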